Table 9-2	Follow up requirements for liver events and laboratory triggers	68
Table 9-3	Specific renal alert criteria and actions	71

List of figures

Figure 3-1	Study design	33
------------	--------------------	----

List of abbreviations

AE	adverse event
ALT	alanine aminotransferase
ALP	alkaline phosphatase
ANCOVA	analysis of covariance
AST	aspartate aminotransferase
b.i.d.	twice per day
BMI	Body Mass Index
BUN	blood urea nitrogen
CD-ROM	compact disc – read only memory
CDS	Core Data Sheet (for marketed drugs)
CFR	Code of Federal Regulations
CK	creatinine kinase
CMO&PS	Chief Medical Office and Patient Safety
CRF	Case Report/Record Form (paper or electronic)
CO ₂	carbon dioxide
CRO	Contract Research Organization
CSR	Clinical Study Report
CTC	Common Toxicity Criteria
CTRД	Clinical Trial Results Database
CV	coefficient of variation
DDI	Drug-drug interaction
DMC	Data Monitoring Committee
DNA	Deoxyribonucleic acid
EC	Ethics committee
ECG	Electrocardiogram
EDC	Electronic Data Capture
eGFR	Estimated glomerular filtration rate
ELISA	Enzyme-linked immunosorbent assay
EORTC	European Organization for Research and Treatment of Cancer
	Commercially Confidential Information
FB	Factor B

FDA	Food and Drug Administration
FIH	First in human
GCP	Good Clinical Practice
GLP	Good Laboratory Practice
GPI	glycosylphosphatidylinositol
γ-GT	Gamma-glutamyl transferase
h	hour
HIV	human immunodeficiency virus
ICH	International Conference on Harmonization of Technical Requirements for Registration of Pharmaceuticals for Human Use
IEC	Independent Ethics Committee
IG	Immonogenicity
IgAN	IgA nephropathy
IgG1	Immunoglobulin G 1
IRB	Institutional Review Board
IRT	Interactive Response Technology
IUD	intrauterine device
IUS	intrauterine system
i.v.	intravenous
LC/MS	Liquid Chromatography/Mass Spectrometry
LDH	lactate dehydrogenase
LFT	Liver function test Commercially Confidential Information
LLN	lower limit of normal
LPS	Lipopolysaccharides
mAb	Monoclonal antibodies
MAC	membrane attack complex
MedDRA	Medical dictionary for regulatory activities
mg	milligram(s)
MN	membranous nephropathy
ml	milliliter(s)
NOAEL	no observed adverse effect level

NOVDD	Novartis Data Dictionary
OC/RDC	Oracle Clinical/Remote Data Capture
PA	posteroanterior
PD	pharmacodynamic(s)
PFT	pulmonary function test(s)
PK	pharmacokinetic(s)
PNH	Paroxysmal nocturnal hemoglobinuria
p.o.	oral(ly)

Commercially Confidential Information

RBC	red blood cell(s)
REB	Research Ethics Board
SAD	single-ascending dose
SAE	serious adverse event
s.c.	subcutaneous
SCC	squamous cell carcinoma
SGOT	serum glutamic oxaloacetic transaminase
SGPT	serum glutamic pyruvic transaminase
SD	standard deviation
SOM	site operations manual
SUSAR	Suspected Unexpected Serious Adverse Reactions
TBL	total bilirubin
ULN	upper limit of normal
ULQ	upper limit of quantification
WBC	white blood cell(s)
WHO	World Health Organization

Pharmacokinetic definitions and symbols

AUC0-t	The area under the plasma (or serum or blood) concentration-time curve from time zero to time 't' where t is a defined time point after administration [mass x time / volume]
AUClast	The area under the plasma (or serum or blood) concentration-time curve from time zero to the time of the last quantifiable concentration [mass x time / volume]
Cmax	The observed maximum plasma (or serum or blood) concentration following drug administration [mass / volume]
Tmax	The time to reach the maximum concentration after drug administration [time]

Commercially Confidential Information

Protocol synopsis

Protocol number	CLFG316X2201
Title	An open-label proof of concept study to assess the efficacy, safety and pharmacokinetics of LFG316, an anti-C5 monoclonal antibody in patients with paroxysmal nocturnal hemoglobinuria (PNH)
Brief title	Proof of concept study to assess the efficacy, safety and pharmacokinetics of LFG316 in patients with paroxysmal nocturnal hemoglobinuria (PNH)
Sponsor and Clinical Phase	Novartis Pharma Services AG Phase II
Intervention type	Biologic
Study type	Interventional
Purpose and rationale	To determine whether LFG316 administered via i.v. infusion can induce a hematological response, as measured by reduction in hemolytic activity, in patients with PNH. Period 4 was implemented to convert PNH patients receiving i.v. infusion of LFG316 to oral treatment with LNP023 in order to enable participation in the planned LNP023 long-term extension study CLNP023C12001B, and to assure continuous treatment of the study patients who otherwise have limited treatment options.
Primary Objective(s)	To assess the effect of LFG316 on the reduction of intravascular hemolysis in PNH patients as determined by measuring changes in serum LDH levels within 4 weeks of treatment and over the entire treatment period.
Secondary Objectives	To assess the tolerability and pharmacokinetics of LFG316 in patients with PNH. Standard safety monitoring with increased vigilance for infections will be applied, and measurement of serum concentrations of LFG316.
Study design	Open-label, non-controlled study in patients with PNH. The study will consist of a 60-day screening period to assess eligibility and conduct vaccinations if required (for all patients not previously vaccinated at least 2 weeks prior to first dosing or if prior vaccination cannot be confirmed). During the treatment period 1, all patients will receive infusions of LFG316 every 14 days. At the end of period 1, efficacy on hemolytic activity by serum LDH will be assessed. All patients will be allowed to enter the optional treatment period 2 and subsequently period 3, and will undergo all assessments specified by the Protocol Assessment Schedule. The extension period 3 will be followed by a Study Completion evaluation approximately 8 weeks after the last drug administration. Patients participating in extension period 3 (up to 260 weeks) will roll over from the last dosing visit of period 2 to the first visit (which includes drug administration) of period 3. The same dosing interval applied in period 1 and 2 needs to be respected between the last dosing visit of period 2 (Week 52 of treatment) and the first visit of period 3. The LFG316 treatment for all patients will be completed by end of 2021 regardless of each individual treatment period. Patients participating in period 3 will have the option to complete the period 3 Follow up and Study Completion evaluation or to continue with study period 4 which is a pre-requisite for their eligibility to join the long-term extension

	
study CLNP023C12001B. During period 4, which will last approximately 21 weeks, treatment will be converted from intravenous LFG316 to oral LNP023. During the first 4 weeks patients will continue to receive LFG316 20 mg/kg every two weeks (total of two administrations) in addition to oral administration of LNP023 200 mg b.i.d. After 4 weeks, patients will discontinue LFG316 and will proceed with LNP023 200 mg b.i.d. for approximately 16 weeks (+/- 28 days).

Population	The study population will be comprised of male and female PNH patients not currently receiving eculizumab therapy and who fulfill all other eligibility criteria.
Key inclusion criteria	
Male and female patients ≥18 years old with a diagnosis of PNH prior to screening. Based on local requirements (applicable in Czech Republic) only patients between the age of 18-65 (inclusive) with a diagnosis of PNH prior to screening may be eligible for inclusion in this study.A documented PNH clone size of ≥10% by RBCs and/or granulocytes, measured by GPI-deficiency on flow cytometrySerum LDH levels at least 1.5-fold above the upper limit of normal (ULN) at screeningNegative pregnancy test for women of child bearing potential at screeningPrevious vaccination against Neisseria meningitidis types A, C, Y and W-135 is required at least 2 weeks prior to first dosing. Vaccination against meningitidis type B should be conducted if available and acceptable by local regulations, at least 2 weeks prior to first dosing. Subjects to be included in this study after protocol amendment 6 also have to fulfill criterion:PNH patients that are carriers of the C5 gene minor variants as defined by nucleic acid changes that lead to amino acid exchanges in position p.Arg885 
Inclusion Criteria for period 4:
 
Patients participating in period 3 of the current study who are willing to join long-term extension study with LNP023 (CLNP023C12001B)Previous vaccination for the prevention of S. pneumoniae and H. influenzae at least 2 weeks prior to first dosing with LNP023 if locally available. If LNP023 treatment has to start earlier than 2 weeks post vaccination, prophylactic antibiotic treatment must be initiated.

Key exclusion criteria	
 Known or suspected hereditary complement deficiency History of recurrent meningitis, history of meningococcal meningitis despite vaccination Presence or suspicion (based on judgment of the investigator) of active bacterial infection within 2 weeks prior to first dose of LFG316, or recurrent bacterial infections Under active therapy with other agents interfering with the complement system Women of child-bearing potential, defined as all women physiologically capable of becoming pregnant, unless they are using highly effective methods of contraception during dosing and for 50 days after the last dose of LFG316.
Investigational and reference therapy	
Periods 1 to 3: LFG316 will be administered via i.v. infusion every 14 days to all patients participating to the study.
 
Period 4: During the first 4 weeks patients will continue to receive LFG316 20 mg/kg every two weeks (total of two administrations) in addition to oral administration of LNP023 200 mg b.i.d. After 4 weeks, patients will discontinue LFG316 and will proceed with LNP023 200 mg b.i.d. for approximately 16 weeks.

Efficacy/PD assessments	Serum LDH
Safety assessments	
Laboratory Evaluations
 
ECG
 
Pregnancy
 
Vital signs / Height and weight

Other assessments	Commercially Confidential Information
Data analysis	
The primary efficacy variable is response rate where a patient will be considered a responder if the percentage reduction from baseline in serum LDH is at least 60% at any time up to and including week 4 for that patient.
 
Thorough verification and analysis of the LDH response will be also conducted on the overall treatment duration.
 
Total LFG316 concentrations will be expressed as $\mu\text{g/mL}$.
 
Commercially Confidential Information
 
All information obtained on adverse events will be displayed as summary and by subject.

Key words	PNH, LFG316, C5, LNP023

1 Introduction

1.1 Background

Paroxysmal nocturnal hemoglobinuria (PNH) is a life threatening condition caused by a somatic mutation in hematopoietic stem cells leading to loss of cell surface complement regulatory proteins (CD55 & CD59) on all progeny cells including red blood cells (RBCs). The deficiency in CD55 & CD59 allows for uncontrolled C3 activation & opsonization of RBCs. Subsequently, assembly of the membrane attack complex (MAC) from Complement factors C5, C6, C7, C8, C9 causes intravascular lysis of RBCs. The resulting paroxysms of hemolysis lead to the release of high amounts of free hemoglobin into the circulation, which is reflected by hemoglobinuria and a drop in circulating haptoglobin. The clinical manifestations of PNH are multifold and include fatigue, abdominal pain and smooth muscle dystonias. The highly elevated risk for thromboembolic events is the most important cause of mortality. Frequent blood transfusions are required to treat anemia in PNH patients experiencing severe episodes of hemolysis.

Commercially Confidential Information

LFG316 is an anti-C5 antibody that binds to a different, remote epitope on C5 compared with eculizumab.

Commercially Confidential Information

Beside the well-described intravascular hemolysis, PNH patients frequently present with persistent extravascular hemolysis despite blockade of the complement Factor C5 leading to continuous red blood cell hemolysis, reactive reticulocytosis, increased bilirubin and LDH levels ([Hill et al 2010](#); [Risitano et al 2009](#)).

LNP023 is a novel oral small molecular weight compound that reversibly inhibits FB of the complement alternative pathway (AP) thereby preventing C3 fragments from opsonizing PNH erythrocytes leading to less extravascular and intravascular hemolysis ([Risitano and Marotta 2016](#); [Subias Hidalgo et al 2017](#)). It is thought that blockade of the AP with oral LNP023 has the potential to prevent both intra- and extravascular hemolysis and therefore offer therapeutic superiority to the anti-C5 therapy.

1.1.1 Relevant data summary

The most relevant data for the present study are summarized in the sections below. For detailed information, please refer to the respective Investigators Brochures.

Commercially Confidential Information

Commercially Confidential Information

1.1.1.3 Human safety and tolerability data

1.1.1.3.1 LFG316

Commercially Confidential Information

Eculizumab was approved in 2007 for the treatment of PNH and in 2011 for atypical hemolytic uremic syndrome. The most important serious safety finding with eculizumab therapy is the increased risk of *Neisseria* infections. Therefore, patients are vaccinated against *N. meningitidis* prior to receiving eculizumab. In some countries, the prophylactic administration of antibiotics is required. Similar measures will be applied in the present study.

1.1.1.4 Human pharmacokinetic data

Commercially Confidential Information

1.1.1.5 Human pharmacodynamic data

Commercially Confidential Information

Commercially Confidential Information

1.2 Study purpose

The purpose of the study is to determine whether LFG316 administered via i.v. infusion at 20 mg/kg once every 14 days can induce a hematological response, as measured by reduction in hemolytic activity, in patients with PNH. Commercially Confidential Information

Period 3 (extension of treatment duration) was implemented to ensure a seamless continuation of treatment for LFG316-responsive patients enrolled in the study.

Period 4 is implemented to convert PNH patients receiving i.v. infusion of LFG316 to oral treatment with LNP023, thereby allowing them to be considered for participation in the planned long-term extension study CLNP023C12001B.

2 Study objectives

2.1 Primary objective(s)

Objective	Endpoint

To assess the effect of LFG316 on the reduction of intravascular hemolysis in PNH patients	
Reduction in serum LDH levels within the first 4 weeks of treatmentReduction in serum LDH levels over the entire treatment period.

2.2 Secondary objective(s)

Objective	Endpoint

To assess the tolerability and pharmacokinetics of LFG316 in patients with PNH	
Standard safety monitoring with increased vigilance for infectionsMeasurement of serum concentrations of LFG316

2.3 Exploratory objective(s)

Commercially Confidential Information

3 Investigational plan

3.1 Study design

This is an open-label, non-controlled study in patients with PNH. Approximately 10 patients will be enrolled in the study. At the time that Protocol amendment v07 is effective, no additional patients will be enrolled. The study drug will be administered via i.v. infusion at the dose level of 20 mg/kg every 14 days. Patients participating in study will have an option to either complete period 3 Follow up and Study Completion evaluation or continue in study period 4 that is pre-requisite to join the long-term extension study CLNP023C12001B, that is separate to this study protocol. Patients who are potentially eligible and willing to participate in the LNP023 long-term extension study will join period 4, where treatment will be converted from LFG316 to LNP023 200 mg b.i.d.

The study will consist of a 60-day screening period to assess eligibility and conduct vaccinations if required (for all patients not previously vaccinated at least 2 weeks prior to first dosing or if prior vaccination cannot be confirmed). An extensive screening window (up to 60 days) is planned in order to comply with local vaccination requirements, if available and deemed necessary at the investigator's discretion. Safety evaluation assessments requiring blood and urine samplings, pregnancy test, pulmonary function test, ECG, patient reported outcomes, and assessment of number of blood transfusions should be performed no longer than 4 weeks prior

to the planned dosing day. Subjects who meet the eligibility criteria at screening will be admitted to baseline (Day 1) evaluations. The patients will enter treatment period 1, and will receive infusions of LFG316 every 14 days, days 1, 15 and 29 (3 administrations).

At the end of period 1, efficacy on hemolytic activity by serum LDH will be assessed. All patients will then be allowed to enter the optional treatment period 2, and will receive infusions of LFG316 every 14 days, and undergo the efficacy, PK, CCI and safety assessments for additional 48 weeks.

Following the 48-week treatment period 2, LFG316-responsive patients (assessed based on investigator's judgment) will be allowed to enter an additional third extension period of up to 260 weeks (extension period 3).

The LFG316 treatment for all patients will be completed by end of 2021 regardless of each individual treatment period.

[figure not shown]
Patients participating in extension period 3 will roll over from the last dosing visit of period 2 to the first visit (which includes drug administration) of period 3. The same dosing interval applied in Period 1 and 2 will be applied between the last dosing visit of Period 2 and the first visit of Period 3.

Period 4 can be initiated as directed by Sponsor and will last approximately 21 weeks. During the first 4 weeks patients will continue to receive LFG316 20 mg/kg every two weeks (total of two administrations) in addition to oral administration of LNP023 200 mg b.i.d. After 4 weeks, patients will discontinue LFG316 and will proceed with LNP023 200 mg b.i.d. monotherapy for approximately 16 weeks (+/- 28 days). Patients who participate in period 4 can join the long-term extension study CLNP023C12001B as soon as their eligibility is confirmed and study CLNP023C12001B is open to receive patients. There should be no LNP023 treatment gap between the studies. Please refer to [Section 7.1](#) for guidance regarding safety monitoring and LNP023 down-titration in case of LNP023 treatment discontinuation.

Commercially Confidential Information

For patients not participating in the period 4, the extension period 3 will be followed by a Study Completion evaluation approximately 8 weeks after the last drug administration. Patients who discontinue treatment prematurely during any of the study periods will be followed for 8 weeks after discontinuation, and will similarly undergo a study completion visit. The 8 weeks follow-up period will start the day after the last drug administration (both for patients completing treatment and patients prematurely discontinuing), and will comprise one visit after approximately 4 weeks, and a study completion visit after approximately 8 weeks from the last drug administration. Safety assessments will include physical examinations, ECG, vital signs, standard clinical laboratory evaluations (hematology, blood chemistry, urinalysis) and adverse event monitoring.

Patients participating in period 4, will complete their Study Completion evaluation approximately one week after last LNP023 treatment administered as a part of this study.

Figure 3-1 Study design

*Period 4 is applicable only for the patients who are potentially eligible and wish to participate in the long-term extension study CLNP023C12001B

**+/-28 days

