11.4.1 Variable(s)

The primary efficacy variable for assessing the effect of LFG316 over the first 4 weeks of treatment is response rate where a patient will be considered a responder if the percentage reduction from baseline in serum LDH is at least 60% at any time up to and including week 4 for that patient.

The primary efficacy variable for assessing the effect of LFG316 over the entire treatment period is the actual serum LDH value measured at multiple time points during the study.

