11.4.2 Statistical model, hypothesis, and method of analysis

Proof of concept will be based on LDH levels during the first four weeks. A positive sign of efficacy is when:

- The estimated median response rate is at least 50%

Commercially Confidential Information

For the analysis of serum LDH values from multiple time points, a longitudinal model analysis of log-transformed LDH levels over time pre- and post-treatment will also be performed.

Longitudinal modelling will include individual and treatment average graphical presentations over time incorporating any historical LDH data collected so as to better put post-treatment changes in context.

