11.4.4 Supportive analyses

For comparison with the Bayesian analysis above, supportive analyses are in the frequentist paradigm giving the possibility of incorporating meaningful prognostic characteristics, such as being carriers or not of the minor allelic variant of C5, in modelling the response rate as binary data in logit models.

Alternative longitudinal model analyses of log-transformed LDH levels over time pre- and post-treatment may also be performed, to assess the sensitivity of the primary analysis to missing data, any deviations from assumptions, and to also assess the impact of prognostic factors on conclusions.

Commercially Confidential Information

Additionally serum LDH at each timepoint will also be summarized in terms of the number and percentage of patients achieving a reduction in LDH to within the normal limits.

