7.1.6 Supportive analyses

Commercially Confidential Information

Longitudinal analysis will firstly include individual and average graphical presentations over time incorporating any historical LDH data collected so as to better put post-treatment changes in context. If deemed potentially useful, longitudinal statistical modelling will be used to look at changes within subjects as well as across subjects.

Additionally serum LDH at each timepoint will also be summarized in terms of the number and percentage of patients achieving a reduction in LDH to within the normal limits.

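### If period 3 admits only patients judged responsive, averages and percentages of LDH can improve after week 52 through selection alone, and the SAP makes the model that would largely correct the mean optional

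*Protocol*

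**What the plan says.** **Entry to period 3.** Protocol section 3.1, repeated in SAP section 2.2, states that "LFG316-responsive patients (assessed based on investigator's judgment) will be allowed to enter an additional third extension period". Section 1.2 gives the matching purpose: period 3 exists "to ensure a seamless continuation of treatment for LFG316-responsive patients enrolled in the study". No LDH criterion is attached to the judgment. The synopsis has a different rule: "All patients will be allowed to enter the optional treatment period 2 and subsequently period 3".

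**Variable.** Section 11.4.1 of the protocol says: "The primary efficacy variable for assessing the effect of LFG316 over the entire treatment period is the actual serum LDH value". SAP section 7.1.1 carries the same definition.

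**Planned summaries.** Protocol section 11.4.4 says that "serum LDH at each timepoint will also be summarized in terms of the number and percentage of patients achieving a reduction in LDH" to within normal limits, and SAP section 7.1.6 repeats this. Neither gives a denominator. SAP section 7.1.6 also says: "Longitudinal analysis will firstly include individual and average graphical presentations over time incorporating any historical LDH data". Protocol section 11.1 and SAP section 5 can be read as presenting periods 1 to 3 together, with only period 4 apart.

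**Planned model.** Protocol section 11.4.2 says that "a longitudinal model analysis of log-transformed LDH levels over time pre- and post-treatment will also be performed". SAP section 7.1.6 makes longitudinal modelling conditional on its being thought useful.

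**Size and length.** Section 3.1: "Approximately 10 patients will be enrolled in the study". Period 3 lasts up to 260 weeks, and its visit schedule runs to week 312.

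**The concern.** Under the rule in section 3.1, entry to period 3 depends on response, and serum LDH is the study's measure of response. A patient who completes period 2 and is not admitted contributes LDH up to week 52 and, on treatment, nothing afterwards. A mean or percentage computed on the patients present at each visit then compares two different groups on either side of week 52.

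The missing-data text does not clearly cover this patient. SAP section 7.1.5 deals with discontinuation before the end of period 1 and with incomplete data. After treatment stops, LDH is followed for eight weeks only, off drug.

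What is at stake is the reading of the second primary variable. Up to 260 of 312 treatment weeks (52 + 260) could come from a group selected on response, and a lower mean or higher percentage there could be taken for a deepening or well-maintained effect.

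**Working it through.** The plan gives no figure to reproduce: the sample-size text is redacted, and no expected number of non-entrants is stated. The check is therefore of the mechanism. Every input below except the 10 patients is an assumption.

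**1. Percentage with normal LDH.** Let N = 10, let m patients have normal LDH, and let k patients without normal LDH not be admitted. Nobody's LDH changes. The available-case percentage moves from m/10 to m/(10 − k). With m = 6:

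| k not admitted | Up to week 52 | After week 52, patients present | After week 52, fixed denominator |
|---|---|---|---|
| 0 | 6/10 = 60% | 6/10 = 60% | 60% |
| 1 | 6/10 = 60% | 6/9 = 67% | 60% |
| 2 | 6/10 = 60% | 6/8 = 75% | 60% |
| 3 | 6/10 = 60% | 6/7 = 86% | 60% |

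The direction depends on who is left out. If the one patient not admitted had normal LDH, the percentage would fall, to 5/9 = 56%.

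**2. Geometric mean.** Let continuing patients sit at 1.2 × ULN and let two others sit at r times that level. The mean for all ten is 1.2 × r^(2/10); for those who continue it is 1.2.

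- r = 2: 1.38 to 1.20 × ULN, an apparent fall of 1 − 2^(−0.2) = 13%
- r = 3: 1.49 to 1.20 × ULN, an apparent fall of 20%
- r = 5: 1.66 to 1.20 × ULN, an apparent fall of 28%

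**3. Chance that anyone is left out.** If each patient is independently judged responsive with probability p, the chance that at least one of 10 is not admitted is 1 − p^10. This is 65% for p = 0.9, 89% for p = 0.8 and 97% for p = 0.7.

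**4. What the model does.** In 300 simulated trials of 10 patients there was no true change over time. Log LDH had a between-patient SD of 0.5 around log(1.5 × ULN) and a within-patient SD of 0.25, with six values per period. Patients entered period 3 if their mean observed log LDH in period 2 was below log(2 × ULN).

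- Raw means: average period 3 / period 2 ratio 0.80, an apparent 20% fall.
- Random-intercept model on all patients: ratio 1.00.

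The model works here because entry depends only on LDH that is in the data. If the judgment rests on unrecorded factors related to later LDH, it need not. It also does not correct the percentage with normal LDH.

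**The case against.** The strongest reply is that the protocol already has the right analysis. Section 11.4.2 commits to the longitudinal model, section 11.4.3 brings available data from early discontinuers into further models, and section 11.4.4 allows alternatives for missing data. This stands for the mean as far as the protocol goes. It is weakened by SAP section 7.1.6, where the averages and percentages are firm and the model is optional.

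Individual LDH plots are also planned, and SAP section 7.1.2 puts N in the summaries. With about 10 patients, flat individual curves beside a falling mean, or a drop in N, would alert a careful reader. This too stands, but it leaves the correction to the reader.

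Text is redacted next to the LDH summaries, the graphics and the analysis sets, so a denominator or a firm model may be set out there. That the summaries use only patients present is an inference from the visible text. So is the link between the investigator's judgment and LDH, though it is plausible given the study's efficacy measure.

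A reader might infer that LDH summaries will improve after week 52, or that the trial's efficacy conclusion is compromised. The documents support neither. No number of non-entrants is given, and under the synopsis rule nobody is excluded for non-response. Proof of concept rests on the first four weeks, before any selection for period 3. The percentage with normal LDH is a supportive summary. The 260 weeks are a maximum, and LFG316 treatment ends for everyone by the end of 2021.

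**Conclusion.** The point holds in conditional form. The documents give two rules for entry to period 3, and they must be reconciled. If the responder rule applies and at least one patient with worse LDH is not admitted, available-case averages and percentages can improve after week 52 with no change in any patient. With 10 patients and 6 normal, one such patient moves the percentage by 7 points and two by 15. The apparent fall in the geometric mean is 13% to 28% when two non-entrants have LDH two to five times that of the others. If everyone enters, the effect is zero.

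The protocol's model would largely remove the artefact for the mean, provided that all treated patients are included and entry depends on observed LDH. The gap is that the SAP does not commit to it, and that neither document states how the percentage is counted. This affects how LDH over the entire treatment period is read, not the four-week criterion. It should be corrected, but it does not undermine the trial's main decision.

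**What to change.** 1. Reconcile the synopsis with protocol sections 1.2 and 3.1 and SAP section 2.2 on who may enter period 3. Which rule is right is not for this review.
2. In SAP section 7.1.6, make the longitudinal model of log LDH on all treated patients mandatory, in line with protocol section 11.4.2.
3. Report all-patient LDH summaries to week 52. Show period 3 in a separate, labelled panel beside the same patients' earlier values.
4. For the percentage with normal LDH after week 52, state the denominator and give two versions side by side. One uses the patients present. The other keeps patients not admitted for non-response in the denominator, counted as not normalised. In the second, patients who left for period 4 or at the end-2021 stop leave the denominator from that point, which assumes that their leaving is unrelated to LDH.
5. Report the number and last on-treatment LDH of patients who did not enter period 3, with the reason where recorded. This also shows whether anyone counted as not normalised in item 4 had normal LDH when last measured.

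The cost is SAP wording, one table and one figure panel. The LDH data are already planned; the visible documents do not show whether the reason for non-entry is captured. Late percentages may look less favourable.
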